phenylalanine) will be started at 4.5 hours and used for the measurement of fibrinogen FSR due to the high turnover rate of fibrinogen Subjects will then eat 2 of either Hort 16A Gold (A) or Hayward Green (B) kiwifruit followed by 100g (cooked weight) ground beef immediately following the second muscle biopsy at T=4.5 hrs. The third muscle biopsy ( $BX_3$ ) will be taken at the end of the study (i.e., at 9.5 hours). The last two muscle biopsies will be used to determine the post-meal muscle protein FSR response. Blood samples will be taken at 0,150, 180, and 270 min before consumption of a test food (the fasted blood samples) and at 290, 310, 330, 360, 390, 420, 450, 480, 510, 540, and 570 min (for fed blood samples) to measure tracer enrichment and plasma responses of amino acids, glucose, and insulin. A total of 15 blood samples will be taken during the study (approximately 90 ml).

Analytical methods. The preparation and subsequent analysis of samples for determination of isotopic tracer enrichment will be carried out by means of gas chromatography-mass spectrometry (GCMS: Models 7890A/5975; Agilent Technologies, Santa Clara CA) as described previously (5, 6). Briefly, 125 ul of 10% sulfosalicylic acid will be added to plasma samples to precipitate protein. Plasma free amino acids will be then extracted from 300 ul supernatant fluid by cation exchange chromatography (Strata-X-C; Phenomenex, Torrance, CA) and dried under Speed Vac (Savant Instruments, Farmingdale, NY). Enrichments of phenylalanine and tyrosine will be measured on the tert-butyldimethylsilyl derivative with the use of GCMS (5, 6). Ions of mass to charge ratios of 234, 235, and 239 for phenylalanine and of 466, 467, 468, and 470 for tyrosine will be monitored with electron impact ionization and selected ion monitoring. Plasma glucose concentrations will be measured spectrophotometrically on a Cobas c 111 analyser (Roche, F. Hoffman-La Roche, Basel, Switzerland). Plasma insulin concentrations will be measured by using commercially available human insulin ELISA kit (Alpco Diagnostics, Salem, MA). Plasma AA concentrations will be determined by using liquid chromatography-mass spectrometry (LCMS: QTrap 5500 MS; AB Sciex) using the internal standard method (6). Preparations of muscle tissue samples obtained from the vastus lateralis muscles will be performed as previously described (5, 6). Phenylalanine tracer enrichment from muscle bound protein will be determined as in plasma analyses.

Calculations of protein kinetics at whole body and muscle levels. Whole body protein kinetics will be calculated based on the determinations of the rate of appearance (Ra) into the plasma of phenylalanine and tyrosine and the fractional Ra of endogenous tyrosine converted from phenylalanine as we have previously described (5, 6, 13). Briefly, the area under the curve (AUC) of plasma enrichments of phenylalanine and tyrosine tracers will be calculated using Graphpad Prism 6 for Mac (Graphpad Software, La Jolla, CA) (5, 6). Whole body protein kinetics will be calculated by dividing kinetic values of phenylalanine by its fractional contribution to protein (4%) (13). For the calculations for whole body protein breakdown rate, contribution of phenylalanine from exogenous meal and tracers infused will subtracted from total Ra. The following equations will be used for the calculations of whole body protein kinetics:

- Total rate of appearance of tracer into plasma  $(R_a) = F / E$
- Fractional Ra of Tyrosine from Phenylalanine (Fractional Ra of Tyr from Phe) =  $E_{Tyr M+4} / E_{Phe M+5}$
- Rate of phenylalanine hydroxylation to tyrosine (Phe hydroxylation rate) = Fractional  $R_a$  of Tyr from Phe x  $R_a$  Tyr
- Protein synthesis rate =  $[(R_a \text{ Phe} \text{Phe hydroxylation rate}) \times 25]$
- Protein breakdown rate = [(*R*a Phe F Phe) x 25 PRO]
- Net protein balance = Protein synthesis rate Protein breakdown rate
- Muscle protein fractional synthesis rate (FSR, %/h) = [( $E_{BP2} E_{BP1}$ )/ ( $E_m \times t$ )] x 60 x 100

In these equations, enrichment (E) is expressed as tracer-to-tracee ratio (TTR) or mole percent excess (MPE), calculated as TTR/(TTR + 1). TTR will be used for calculations of rates of protein breakdown whereas MPE will be used for calculations of rates of protein synthesis. E is enrichment of respective tracers. *F* is the tracer infusion rate into a venous site: *F* Phe for phenylalanine tracer. E Tyr M+4 and E Phe M+5 are plasma enrichments of tyrosine tracer at M+4 and of phenylalanine tracer at M+5 relative to M+0, respectively. The correction factor of 25 is for conversion of kinetic

value for phenylalanine to protein based on the assumption that contribution of phenylalanine to protein is 4% (100/4 = 25) (2). PRO is the amount of exogenous protein (g) that is the amount of amino acids appearing in the circulation as a result of the exogenous protein digestion, accounting for splanchnic extraction (29%) of amino acids in young adults (11). Phe hydroxylation rate is the rate of appearance of tyrosine derived from phenylalanine through process of hydroxylation. Calculation of muscle protein FSR will be performed as previously described (5, 6).  $E_{BP1}$  and  $E_{BP2}$  are the enrichments of protein bound L-[*ring*-H5]-phenylalanine in the first and second muscle biopsies, respectively, and  $E_m$  is the mean plasma enrichment of the L-[*ring*-H5]-phenylalanine. *t* is the duration of time in minutes elapsed between two muscle biopsies; 60 and 100 are factors used to express muscle protein synthesis in percent per hour.

Statistical analysis and power calculations. Where effects of both the intervention and time require analysis, a two-way analysis of variance (ANOVA) model with repeated measures will be used. When significant differences between the interventions were identified by ANOVA, post-hoc Student's t-tests will be performed. When analysis involves the comparison of the total response to each intervention only, paired student's t-tests will be used. For all comparisons, statistical significance will be set at p < 0.05.

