## DESIGN AND METHODS

Our **specific hypothesis** is that the consumption of 2 Hayward green kiwifruit (containing actinidin protease) prior to 100g of ground beef will increase the rate of protein digestion from the beef in the elderly, leading to an increased uptake of the essential amino acids. Furthermore, this increased essential amino acid availability will produce a greater postprandial net anabolic protein response, as well as increased fractional synthetic rates of muscle and liver proteins.

To test this hypothesis we will use a double-blinded crossover design involving two intervention arms; in both arms 100g of ground beef (cooked weight) will be consumed following either 2 Hayward green kiwifruit (containing actinidin protease) or 2 Hort16A Gold kiwifruit (devoid of actinidin protease) by elderly subjects.

In response to the interventions, our primary endpoints are:

- the rate of beef protein digestion in the stomach (7);
- plasma amino acids (AA) which will reflect dietary digestibility and availability of precursors for protein synthesis (1);
- the magnitude of the whole-body net anabolic response (NAR), defined as the difference between whole body protein synthesis and protein breakdown, to determine overall protein balance, accounting for all roles of protein in the body (4, 13);

[figure not shown]
and our secondary endpoints are:

- the muscle fractional synthetic rate (FSR) on muscle protein synthesis (4, 13);
- the fibrinogen FSR to determine the impact of actinidin-assisted protein digestion on liver protein synthesis ([name], unpublished research);
- plasma glucose and insulin which will reflect the wider metabolic response (12).

These endpoints will enable achievement of the four objectives summarised in Table 1 on the second page of this proposal.

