#### **Experimental Overview and Rationale:**

We will study a total of 15 healthy male and females between 60 and 85 years of age in a doubleblinded crossover design composed of two intervention arms, as detailed in Figure 3. With a sample size of N=15 subjects, the crossover design will have 80% power to detect a significant effect, where statistical significance is set at p<0.05. The 60-85 year age group was chosen due to the significant loss of muscle mass apparent at this stage of aging, which will provide a backdrop for the most pronounced effects and thus most scientifically accurate measurements. The entire study will take place at University of Arkansas for Medical Sciences (UAMS), in collaboration with [name]. [name] is an international expert in the use of stable isotope tracer technology for the measurement of protein metabolism and developed a majority of the methods considered to be gold-standard for this work. As this is a clinical study with complex methodology, completion of the experimental portion at UAMS under the supervision of [name] and his highly experienced team, will ensure that all procedures are conducted in the manner required for maximum accuracy and sensitivity of the data.

**Figure 3.** Complete outline of crossover design showing phases of study for a subject undergoing treatment A first and treatment B second.

Study Interventions. The interventions are as follows:

- A. 100g of ground beef plus 2x Hort 16A Gold kiwifruit (Control)
- B. 100g of ground beef plus 2x Hayward Green kiwifruit

The studies are referred to as Study A and Study B, respectively, in Figure 3. These amounts were chosen because 100g beef is the recommended serving size of beef for the elderly and we know from previous work that 100g of beef will induce a robust anabolic response (5, 6). Two Hayward Green, but not Hort16A Gold, kiwifruit had a significant effect on the rate of digestion of beef protein in pig trials (7). Ground beef will be produced to have an average protein composition of 25% (10); as 35g of protein is likely to saturate the muscle synthetic response, 25g will be within the range that permits detection of a difference in muscle protein synthetic rate between interventions. The use of ground beef will also limit any effects of masticatory differences between individuals. Subjects will also be selected to ensure masticatory function has not deteriorated.

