Each subject will undergo both interventions, eating either Hort16A Gold fruit for the first arm and Hayward Green fruit for the second arm, or vice versa. Neither subjects nor meal distributors will be informed as to which kiwifruit variety contains actinidin; the study is therefore double-blinded.

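### The crossover analysis has no period term although 15 subjects are randomised to two orders with no stated balancing, and the ANOVA-gated follow-up t-tests are neither called paired nor corrected

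*Combined protocol and SAP*

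**What the plan says.** Experimental Overview and Rationale sets the size: "With a sample size of N=15 subjects, the crossover design will have 80% power". Each subject takes both fruits, "eating either Hort16A Gold fruit for the first arm and Hayward Green fruit for the second arm, or vice versa". The screening-visit paragraph after the exclusion criteria has a coordinator assign subjects at random to group A or B. It gives no ratio, block or other means of balancing the orders.

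The paragraph on statistical analysis and power names two analyses. For time courses: "Where effects of both the intervention and time require analysis, a two-way analysis of variance (ANOVA) model with repeated measures will be used". For overall responses: "When analysis involves the comparison of the total response to each intervention only, paired" Student's t-tests. Neither contains a period or sequence term. Time here is sampling time within a study day, which is how the tracer infusion section uses it, and not the crossover visit.

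On follow-up: "When significant differences between the interventions were identified by ANOVA, post-hoc" Student's t-tests are done. On the significance level: "For all comparisons, statistical significance will be set at p < 0.05". No multiplicity method is named. The tracer infusion section lists 11 blood samples after the meal.

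**The concern.** The two study days are weeks apart, with a feeding phase and a washout between them, so a general shift from the first visit to the second is possible. Fifteen subjects cannot divide equally between two orders, so such a shift does not cancel fully from the mean within-subject difference. It also spreads the two order groups apart, and the paired t-test counts that spread as noise. At a near-even split the cost is power. At an uneven split part of the shift is credited to the fruit.

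The follow-up tests raise a separate issue. The hypothesis is that Green kiwifruit "will increase the rate of protein digestion from the beef in the elderly", "leading to an increased uptake of the essential amino acids". A faster rate would appear as a difference at some sampling times and not others. In that situation the ANOVA gate opens for a real reason, and uncorrected tests can then report differences at times where there are none.

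**Working it through.** **Inputs from the documents.** N = 15; two orders; 80% power; 0.05 for every comparison; 11 post-meal times. **Not in the documents:** the endpoint, effect and SD behind the 80%; any period effect; the correlation between times; dropout. I assume two-sided tests and complete data.

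**1. The stated power.** The 80% cannot be reproduced without an effect and an SD, so I back-solve it. A paired t-test with 14 df has 80% power when d × √15 = 0.778 × 3.873 = 3.01. The implied effect is d = 0.778 SD of the within-subject difference, and I use it throughout.

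**2. Effect of a shift on the paired test.** Let D = Green minus Gold, with treatment effect δ and visit-2-minus-visit-1 shift π, both in SDs of D. Subjects with Gold first (n1) have mean D of δ + π; those with Green first (n2) have δ - π. So:
- mean of D = δ + π(n1-n2)/15
- expected sample variance of D = 1 + π² × 4·n1·n2/(15 × 14)

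At 8/7 with π = 0.5, the bias is 0.5 × 1/15 = 0.033 and the variance is 1 + 0.25 × 224/210 = 1.27.

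**3. Period-adjusted comparison.** Average the two sequence means of D. The standard error is 0.5 × √(1/n1 + 1/n2), with 13 df. At 8/7 this is 0.5 × √(1/8 + 1/7) = 0.2588, against 1/√15 = 0.2582 for the paired test.

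**4. Results by split.** Probabilities assume unrestricted 1:1 randomisation, Binomial(15, 0.5). Type I error is simulated with 200,000 runs per cell.

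| Split | Probability | Bias, share of shift | Paired type I error at π = 0.5 | Adjusted power, no shift |
|---|---|---|---|---|
| 8/7 | 39% | 1/15 | 3% | 79.4% |
| 9/6 | 31% | 3/15 | 4% | 77.9% |
| 10/5 | 18% | 5/15 | 6% | 74.7% |
| 11/4 | 8% | 7/15 | 10% | 69.3% |

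A split of 10/5 or worse has probability 30%, and 11/4 or worse 12%. Averaged over all splits, the paired type I error at π = 0.5 is about 5%. The adjusted test holds 5% at each split.

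Power, paired against adjusted (ranges depend on which order has the extra subject):

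| Shift | 8/7 split | Averaged over unrestricted randomisation |
|---|---|---|
| none | 80.0% v 79.4% | 80.0% v 76.4% |
| 0.25 SD | 76-80% v 79% | 77.6% v 76.6% |
| 0.5 SD | 68-76% v 79% | 70.9% v 76.6% |

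**5. Follow-up tests.** If there is no effect at any time, gating on the ANOVA intervention main effect keeps the chance of any false time-point finding at about 3.5-5%. Now let the first two post-meal times differ by 0.778 to 1.5 SD and the other nine not. Assumed: AR(1) correlation 0.6 or 0.8 between successive samples, residual SD 0.2, subject-by-arm SD 0.12, 20,000 runs. The chance of at least one false difference among the nine is:
- 7-12% if the main effect opens the gate; about 2% with Holm over the 11 times
- 18-27% if a significant intervention-by-time interaction opens it; 3-4% with Holm

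Holm lowers power at one truly different time from 80% to 41% at 0.778 SD, from 95% to 69% at 1.0 SD, and from 100% to 98% at 1.5 SD.

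**The case against.** **The harm from the missing period term is conditional.** No period effect is documented. At a 0.5 SD shift the paired test is conservative at 8/7 and 9/6, which together make up about 70% of unrestricted allocations (39% + 31%). Without blocking, the period term lowers average power unless the shift exceeds about 0.25 SD. All of this stands. A reader might infer that the trial's false-positive rate is inflated. The documents do not support that: it is inflated only if a sizeable shift meets an uneven split, and it averages about 5%. The objection is also why the period term should come together with blocking.

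**The follow-up tests are gated.** They run only after a significant ANOVA difference between interventions, and that wording leans towards the main effect. A reader might take the ungated rate for 11 tests (21-28% in the scenario of step 5) as the plan's error rate. It is not, because the plan has a gate. What remains is that the gate gives no protection across times once a real effect has opened it.

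**The plan does not say the follow-up is at each sampling time, or that it is unpaired.** Both are true. With two interventions, a t-test of the overall difference would repeat the ANOVA, so time-point comparison is the only informative reading, but it is an inference. The word paired is attached only to the total-response tests, so its absence here is a gap and not a declared choice of unpaired tests.

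**The plan does not offer two chances on one endpoint.** A reader might infer that either the ANOVA or the total-response test may be accepted for the same analyte. The text assigns them to different situations, so no error rate should be charged for that.

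**Conclusion.** The concern holds as a cheap improvement. It does not show that the trial's conclusion is at risk. The stated analyses omit a period term in a crossover whose orders cannot be equal and are not stated to be balanced. With an 8/7 split and a 0.5 SD shift, this costs about 3 to 11 points of power (79% against 76% or 68%), with negligible bias. Material bias and a type I error of 6-10% need a split of 10/5 or 11/4 as well as that shift.

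Once a real early effect has opened the gate, the follow-up tests falsely mark at least one other time in about 7-12% of trials under the main-effect reading, and 18-27% if a significant interaction opens it.

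The missing period term, balancing and correction can be read directly from the text. The sizes rest on assumptions: the back-solved effect, the size of the shift, unrestricted randomisation, the correlation between times, and which times truly differ.

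**What to change.** 1. Allocate order from a blocked list that yields 8 subjects in one order and 7 in the other.
2. Replace the paired t-test with the period-adjusted crossover comparison: the mean of the two sequence means of within-subject differences, with 13 df if all 15 complete. It remains free of period bias if dropout changes the split. In the repeated-measures ANOVA, add sequence as a between-subject factor with unweighted sequence means, so that intervention-by-sequence is the period term.
3. State that the follow-up tests are made at the post-meal sampling times and are paired. Either Holm-correct them over the 11 times or label them descriptive.

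**Cost.** Wording, an allocation list and a different model call on data already planned. If there is no shift, the period term costs 80.0 - 79.4 = 0.6 points of power at 8/7. Without blocking it costs about 3.5 points on average, so blocking is part of the fix. Holm roughly halves power at a single time for an effect of 0.778 SD (80% to 41%). That is acceptable because these tests only locate a difference; labelling them descriptive avoids the loss.
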